4.5 Rescue Medication Administration

If at any point the patient expressed inadequate analgesia and the treating provider wants to administer a new pain drug, they will be eligible to do so however that will be marked as “Insufficient pain relief”. The patient can continue with the study unless at any point they wish to withdraw. Rescue medication will be administered at the discretion of the treating physician or advance practice provider. Rescue medication will not be lidocaine and will never be given to a patient more than once in this study.

4.6 Subject Completion/Withdrawal

Subjects may withdraw from the study at any time without prejudice to their care. They may also be discontinued from the study at the discretion of the Investigator if it is later discovered that they have any exclusion criteria, as determined by chart review or “Care Everywhere”. If the Investigator becomes aware of any serious, related adverse events after the subject completes or withdraws from the study, they will be recorded in the source documents and on the CRF and reported to the IRB.

4.6.1 Early Termination Study Visit

If a subject wishes to withdraw from the study, their entire study packet will be kept but not used for any study related analysis. The subject will be marked in REDCap as withdrawing from study but no statistical analysis will be undertaken.

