Study Duration	Each subject's participation will last one week. The entire study is expected to last twelve months.
Study Phases Screening	This study will have three phases. Screening and intervention will occur on the same day in the emergency department. Follow up will occur 7 days later.

Intervention	
Follow-Up	
Efficacy Evaluations	The primary outcome for this study will be mean pain score improvement after 90 minutes from administration of study drug.
Pharmacokinetic Evaluations	Not applicable
Safety Evaluations	Patient reported side effects, medications required to treat side effects, administration of naloxone, change in disposition attributed to study drug and incidence of any serious adverse events.
Statistical And Analytic Plan	Intention to treat. Statistical analysis will be primarily t-tests and chi-square tests.
Data And Safety Monitoring Plan	A DSMB will be in place.

TABLE 1: SCHEDULE OF STUDY PROCEDURES

TABLE 1: SCHEDULE OF STUDY PROCEDURES (CONTINUED)

FIGURE 1: STUDY DIAGRAM

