6.2 Secondary Endpoints

Secondary endpoints will include the following:

- The mean pain improvement at time 15, 30, 60, 120, 150 and 180 minutes (using same test as primary end point).

- Difference in proportion of patients with adverse events, who experience serious adverse events, require medication to treat adverse events, report insufficient pain relief, require naloxone, have a change in disposition, and a missed diagnosis will be evaluated using a Chi-Square test with an alpha level of 0.05.
- Proportion of patients who prefer to receive the same drug at a future visit will be compared as proportions using a Chi-Square test with an alpha level of 0.05.

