6.2.4 Safety Analysis

All subjects entered into the study will be included in the safety analysis, with the exception of those who wish to withdraw from the study. The frequencies of AEs by type will be summarized. Serious adverse events will be described in detail. Incidence of all safety outcomes will be summarized along with the corresponding exact binomial 95% two-sided confidence intervals.

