6.4 Interim Analysis

The decision to stop the study for efficacy or safety will be primarily determined by the Data Safety Monitoring Board (DSMB). After 94 patients have been enrolled, they will complete an interim analysis.

The stopping boundary for efficacy will be met if the P-value using a t-test for the difference between groups in the primary outcome is 0.001 or less. Using this conservative

Haybittle-Peto boundary ($P \leq 0.001$) will allow the final analysis to be performed using an unchanged level of significance.

The stopping boundary for safety will be met if the P-value using a chi-square test for the difference between groups in the serious adverse event outcome is 0.025 or less.

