8.3 Definition of an Adverse Event

An adverse event is any untoward medical occurrence in a subject receiving a test article and which the occurrence does not necessarily have a causal relationship with the treatment. An adverse event can therefore be any unfavorable and unintended sign (including an abnormal laboratory finding), symptom, or disease temporally associated with the use of the test article, whether or not related to the product.

All AEs (including SAEs) will be noted in the study records and on the case report form with a full description including the nature, date and time of onset, determination of non-serious versus serious, intensity (mild, moderate, severe), duration, causality, and outcome of the event.

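### Sections 4.6.1 and 6.2.4 drop data already recorded for patients who withdraw, which contradicts intention to treat and can understate adverse event and SAE rates

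*Combined protocol and SAP*

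**What the plan says.** The Statistical And Analytic Plan row of the synopsis reads "Intention to treat. Statistical analysis will be primarily t-tests and chi-square tests". It gives no modified definition and no exception.

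Section 4.6 provides that "Subjects may withdraw from the study at any time without prejudice to their care". Section 4.5, on rescue medication, adds that "The patient can continue with the study unless at any point they wish to withdraw". For a patient who withdraws, section 4.6.1 directs that "their entire study packet will be kept but not used for any study related analysis"; the patient is flagged in REDCap and left out of the statistics. Section 6.2.4 puts everyone entered into the safety analysis "with the exception of those who wish to withdraw from the study".

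The comparisons affected are in sections 6.2 and 6.4. Section 6.2 compares by chi-square the proportions with adverse events and with SAEs, and those who "require medication to treat adverse events, report insufficient pain relief, require naloxone", among other outcomes. In section 6.4, after 94 patients, the safety boundary is met if the chi-square P-value for the "difference between groups in the serious adverse event outcome is 0.025 or less".

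**The concern.** Intention to treat keeps randomised patients in the comparison, in their assigned arm. Sections 4.6.1 and 6.2.4 take out randomised patients because of something that happens after randomisation, and they take out observations that exist. This is different from missing data: the values are on file and are set aside.

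The removal may be related to outcome. A patient who has an unpleasant adverse event may ask to leave the study. So may a patient in continuing pain; section 4.5 mentions withdrawal in the same paragraph as the mark for insufficient pain relief, which is itself a secondary endpoint. If patients withdraw for these reasons, the events and failures that prompted withdrawal leave the comparison with them. Comparative safety is the stated secondary objective, and SAEs are likely to be few, so one or two deleted patients could matter.

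**Working it through.** **1. The texts side by side.** The synopsis states intention to treat without exception. Section 4.6.1 excludes the withdrawn patient's whole packet from all analysis. Section 6.2.4 excludes the same patients from the safety analysis. No section reconciles these statements.

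**2. What is lost.** Participation runs to the day-7 call (sections 3.3.1 and 4.3), and withdrawal is possible throughout. A patient followed for 180 minutes who withdraws at that call loses every recorded pain score, including the 90-minute score that defines the primary endpoint (section 6.1), and every recorded adverse event.

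**3. Do other provisions put the data back?** Section 8.3 says "All AEs (including SAEs) will be noted in the study records and on the case report form". Sections 4.6 and 8.5 send SAEs to the IRB, and section 9.1.3 lets the DSMB request unblinded data to analyse an SAE. These protect the reporting of individual cases. None returns a withdrawn patient to the proportions in section 6.2 or to the interim test in section 6.4.

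**4. The loss allowance.** The sample size in section 6.3 reproduces. With SD 3, difference 1.3, two-sided alpha 0.05 and 80% power, the exact t-test solution is 84.57, so 85 per arm; 2 × 85 = 170 and 170 × 1.10 = 187. The 10% allowance protects power. It does not protect against selective removal.

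**5. Effect on a final rate.** With e patients having an event among n, and w withdrawals of whom e_w had the event, the reported rate is (e − e_w)/(n − w). The event and withdrawal counts below are assumptions; n = 93 is about half of 187.

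- SAEs: e = 5, w = e_w = 2. True 5/93 = 5.4%; reported 3/91 = 3.3%.
- Adverse events: e = 19, true 19/93 = 20.4%. With w = e_w = 5, reported 14/88 = 15.9%. With w = 9 (about the 10% loss, all taken as withdrawals), reported 10/84 = 11.9% if all nine had an event and 19/84 = 22.6% if none did.

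The rate is therefore understated when events are more common among those who withdraw than in the rest of the arm, and overstated when they are less common.

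**6. Effect on the interim SAE test.** Assume 47 per arm, an uncorrected Pearson chi-square, and no SAEs in the second arm. With a events in the first arm, arm sizes n1 and n2, and N = n1 + n2, the statistic is N·a·n2 / [n1·(N − a)].

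| Situation | Counts | Chi-square | P | 0.025 met? |
|---|---|---|---|---|
| 5 vs 0, all kept | 5/47 vs 0/47 | 94×5×47/(47×89) = 5.28 | 0.0216 | yes |
| one of the five deleted | 4/46 vs 0/47 | 93×4×47/(46×89) = 4.27 | 0.0388 | no |
| 6 vs 0, all kept | 6/47 vs 0/47 | 94×6×47/(47×88) = 6.41 | 0.0114 | yes |
| one of the six deleted | 5/46 vs 0/47 | 93×5×47/(46×88) = 5.40 | 0.0201 | yes |
| two of the six deleted | 4/45 vs 0/47 | 92×4×47/(45×88) = 4.37 | 0.0366 | no |

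Section 6.4 does not say whether the chi-square is continuity-corrected. With the correction, 5 vs 0 gives P = 0.066 and misses the boundary even with everyone kept; the switch then occurs at 7 vs 0 (P = 0.0184 kept, 0.0325 after one deletion).

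**The case against.** The strongest objection is that the withdrawn group is narrow and may consist of people who refuse use of their data. Treatment is one short infusion. Rescue is not withdrawal (section 4.5), and neither is leaving before 180 minutes (sections 4.4 and 9.4.2). What remains is patients who ask to leave the study, and section 4.6.1 may simply honour a consent promise. The consent pages were not available. This stands as a limit on size and on how much the fix would restore. It does not remove the conflict, because the plan does not separate stopping participation from refusing use of data already given.

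Section 6.2.4 could also be read as an openly stated definition of the safety set, which makes the clearest conflict the one between the synopsis and section 4.6.1. That is fair as to wording, but the safety comparison still loses recorded events.

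The interim illustration is fragile. It sits at the edge of the boundary and depends on the continuity correction. Expected SAE counts are 2.5 per arm at 5 vs 0, and Fisher's exact P is 0.056 both for 5/47 vs 0/47 and for 4/46 vs 0/47. The assumed split has no support in the documents; section 1.2.2.2 reports no SAEs in the earlier trial of these two drugs. The DSMB also has discretion and can request unblinded data. All of this stands, so the table shows only that the rule can change the planned test.

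Finally, section 4.4 replaces a missed numerical secondary outcome with the average of its neighbours. That needs a later measurement, so scores due after withdrawal stay missed. They lie outside this point, which concerns data that were recorded.

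**Conclusion.** The concern holds. The plan states intention to treat and then excludes randomised patients with recorded data from every analysis, including safety. The conflict and the loss of recorded data are clear from the text. The size of the effect is unknown, because the documents give no withdrawal counts or reasons, and it may be small.

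Understatement of harm is conditional on withdrawal being associated with adverse events. The numerical illustrations rest on assumed counts, equal interim arms and an uncorrected chi-square. No size is claimed for the efficacy comparison. The harm is to the compared rates and the interim SAE test, not to the reporting of individual SAEs. The plan should be corrected, since the defect is certain and the remedy is cheap.

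**What to change.** Reconcile the synopsis with sections 4.6.1 and 6.2.4. The two sections should state that:

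- all randomised patients are analysed in their assigned arm, using data recorded up to withdrawal;
- all dosed patients enter the safety analysis and the interim SAE comparison on the same basis;
- the only exception is a patient who refuses use of data already recorded;
- withdrawals and refusals are reported by arm, with reasons.

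Check the consent wording first. If it bars use of the data after withdrawal, state the exception to intention to treat openly and report the excluded patients by arm as counts.

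The cost is a few sentences and slightly more analysis work. The packets are already kept and withdrawals already flagged in REDCap, so no new data collection is needed, and the sample size stays at 187.

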5 STUDY EVALUATIONS AND MEASUREMENTS

5.1 Screening and Monitoring Evaluations and Measurements

5.1.1 Medical Record Review

Include a listing of the variables that will be abstracted from the medical chart (paper or electronic).

- Date of birth
- Biologic sex
- Height (inches)
- Weight (kilograms)
- Medical history (diabetes, hypertension, high cholesterol, coronary artery disease, heart failure)

5.1.2 Vital Signs

All vital signs will be recorded off the patients monitor. Blood pressure will be automated and set to record at the required intervals. The arm without the IV in it will be used for placement of the blood pressure cuff. Measurements will be taken while the patient is laying down in the supine position. If more than one blood pressure is recorded (in the event of an abnormal blood pressure), the one thought to be more accurate will be documented (as determined by the physician or advanced practice provider).

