To summarize the available data on intravenous lidocaine dosed at 2 mg/kg or higher, most studies have been done in the operating room and one has been done in the emergency department. The only study with any significant adverse events was in the first trial done by Kasten et al. These events were hemodynamically significant hypotension. However, all of these patients had critical ischemic heart disease (proven by angiography), had received a beta blocker that day, and shortly before receiving the study drugs, received morphine and lorazepam. Furthermore, neither group received intravenous lidocaine by itself, it was fentanyl with or without intravenous lidocaine. Finally, the dose they chose was 3 mg/kg, significantly higher than the dose we are proposing. The rest of the studies show, at a minimum, improved analgesia compared to placebo and at best, superior analgesia to morphine.

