3 INVESTIGATIONAL PLAN

3.1 General Schema of Study Design

Patients presenting to the emergency department with abdominal pain will be screened for eligibility. Once deemed eligible, they will be randomized to receive either intravenous lidocaine or hydromorphone. The patient, ED nurse and physician will all be blinded to the study drug. Only the research pharmacist will know the drug that the patient is receiving. Primary and secondary endpoints will be measured from the time just before the patient receives the study drug and for the next 180 minutes then once again 7 days later (please refer to Table 1 for timing and specific data being measured). The two drugs will then be compared against one another.

Much of each patient's care will be "standard of care", most likely to include intravenous access, venipuncture, labs, imaging, and potentially consultations by other services. Please refer to Figure 1 for an illustration of study interventions. Standard care can take place at anytime on Figure 1.

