4.2 Study Intervention

4.2.1 Time Zero

- Pain score (1-10)
- Patient placed on monitor
- Vital signs recorded (heart rate, respiratory rate, systolic blood pressure, diastolic blood pressure, pulse oximetry, source of oxygen)
- Study drug administered by patient's nurse (mixed by research pharmacist and sent to the nurse) over 5 minutes

4.2.2 15 minutes after the study drug was started (not after it finished), up to a 15 minute delay will be tolerated

- Pain score
- Vital Signs (same as above)
- Recording of any new symptoms (classified at this point as adverse events)
- Recording of sufficient pain relief (yes or no)
- Recording of any medications to treat adverse events (yes or no). If yes, document was medication was administered, why, and when.
- Recording on whether or not naloxone has been administered (yes or no)
- Recording of any change in disposition thought to be due to study drug (yes or no)
- Recording of any serious adverse event (yes or no)

4.2.3 30 minutes after the study drug was started (not after it finished), up to a 15 minute delay will be tolerated

- Pain score
- Vital Signs (same as above)
- Recording of any new symptoms (classified at this point as adverse events)
- Recording of sufficient pain relief (yes or no)
- Recording of any medications to treat adverse events (yes or no)
- Recording on whether or not naloxone has been administered (yes or no)
- Recording of change in disposition thought to be due to study drug (yes or no)
- Recording of any serious adverse event (yes or no)

4.2.4 60 minutes after the study drug was started (not after it finished), up to a 15 minute delay will be tolerated

- Pain score
- Vital Signs (same as above)
- Recording of any new symptoms (classified at this point as adverse events)
- Recording of sufficient pain relief (yes or no)
- Recording of any medications to treat adverse events (yes or no)
- Recording on whether or not naloxone has been administered (yes or no)
- Recording of change in disposition thought to be due to study drug (yes or no)
- Recording of any serious adverse event (yes or no)

4.2.5 90 minutes after the study drug was started (not after it finished), up to a 15 minute delay will be tolerated

- Pain score
- Vital Signs (same as above)
- Recording of any new symptoms (classified at this point as adverse events)
- Recording of sufficient pain relief (yes or no)

- Recording of any medications to treat adverse events (yes or no)

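### An abnormal blood pressure can be left out of the record on clinician judgement, and symptomless vital-sign abnormalities have no planned place in the safety comparison

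*Combined protocol and SAP*

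**What the plan says.** - **Choice of reading (5.1.2).** Where the pressure has been taken more than once, the text reads "in the event of an abnormal blood pressure), the one thought to be more accurate will be documented". The decision rests with the treating clinician. No criterion for accuracy is given, and nothing says that the other reading is kept.
- **What is measured (4.2.1, repeated in 4.2.2 to 4.2.8).** "Vital signs recorded (heart rate, respiratory rate, systolic blood pressure, diastolic blood pressure, pulse oximetry, source of oxygen". This is done at 0, 15, 30, 60, 90, 120, 150 and 180 minutes, which makes eight time points.
- **What is prompted as an adverse event (4.2.2 to 4.2.8).** "Recording of any new symptoms (classified at this point as adverse events" is the item at each of the seven post-dose records. The synopsis likewise lists patient-reported side effects among its safety evaluations and does not mention vital signs.
- **What an adverse event is (8.3).** "An adverse event can therefore be any unfavorable and unintended sign (including an abnormal laboratory finding), symptom, or disease". The same section requires all adverse events to go on the case report form.
- **Monitoring (5.2).** Vital signs are named as one source for monitoring subject safety.
- **Analysis (6.2 and 6.2.4).** The comparisons cover adverse events, serious adverse events, treatment given for adverse events, insufficient relief, naloxone, disposition and missed diagnosis. There is no vital-sign endpoint, limit or by-arm summary.
- **Blinding (3.1).** "The patient, ED nurse and physician will all be blinded to the study drug".

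**The concern.** Section 2 sets out to show that lidocaine matches hydromorphone on safety as well as on pain relief. The protocol's own background points to haemodynamic and respiratory effects. In the one cited study with significant adverse events, Section 1.2.2.2 says "These events were hemodynamically significant hypotension". The same section reports bradycardia on lidocaine in another study, and 3.1.2 mentions respiratory depression with hydromorphone. These effects are seen first in blood pressure, heart rate and oximetry, and may cause no complaint.

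The plan collects those measurements and then does not use them in the comparison. For blood pressure it also allows an abnormal value to go unrecorded. A finding of similar adverse event proportions would then rest largely on what patients reported, and could not be read as covering symptomless changes in vital signs. A blood pressure that was never documented cannot be recovered at the analysis stage.

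**Working it through.** The plan gives no figure on this point, so there is none to reproduce. The sample size in 6.3 concerns the pain endpoint and plays no part here.

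**Step 1. What the rule in 5.1.2 can remove.** It applies to blood pressure only, and only when there is more than one reading. A single abnormal reading is kept. If the readings are all abnormal, an abnormal one is kept. The case at risk is an abnormal reading followed by a normal one that the clinician judges more accurate. Because the stated occasion for a repeat is an abnormal value, the value at risk is usually the abnormal one, whether low or high.

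**Step 2. Where each kind of finding goes.**

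| Finding at a time point | Value in the record? | Prompted as an adverse event in 4.2? | Other route into the 6.2 comparison |
|---|---|---|---|
| Low pressure, repeat normal and preferred, no symptoms | Not required | No | Only if treated, serious or disposition changes |
| Low pressure, kept, no symptoms | Yes | No (8.3 would allow it) | Same |
| Bradycardia or desaturation, no symptoms | Yes | No (8.3 would allow it) | Same |
| Any of these with symptoms | As above | Yes | Already counted |

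The gap is therefore the symptomless, untreated, non-serious abnormality. Blood pressure can be lost at two stages (record and comparison). Heart rate and oximetry can be lost only at the second.

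**Step 3. Direction.** Let the true proportions of patients with such an event be p1 and p2, and let a fraction c be captured in both arms. The observed difference is c·p1 − c·p2 = c(p1 − p2). Any c below 1 shrinks it.

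**Step 4. Illustration.** The documents give neither event rates nor capture fractions, so both are assumptions. Take n = 93 per arm (187/2 = 93.5, rounded down) and a two-sided 0.05 test of two proportions, with

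power = Φ{[Δ − 1.96·√(2p̄(1 − p̄)/n)] / √([p1(1 − p1) + p2(1 − p2)]/n)},

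where p1 and p2 are the captured proportions, Δ is their difference and p̄ their mean.

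| Captured fraction c | 10% vs 2%: difference, power | 20% vs 5%: difference, power |
|---|---|---|
| 100% | 8 points, 63% | 15 points, 88% |
| 75% | 6 points, 51% | 11.25 points, 75% |
| 50% | 4 points, 36% | 7.5 points, 56% |
| 25% | 2 points, 20% | 3.75 points, 31% |

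For example, at 10% vs 2% with c = 50%, the captured proportions are 5% and 1%, so Δ = 0.04 and p̄ = 0.03. Power = Φ[(0.04 − 0.0490)/0.0248] = Φ(−0.36) = 36%. The normal approximation is rough at such small counts. The table shows the direction for one type of event and does not predict the loss in this trial.

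**The case against.** The case on the other side has real weight, and several parts of it stand.

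- **Section 8.3 already counts signs.** It defines them as adverse events and sends all adverse events to the case report form, and 5.2 names vital signs. A reader might infer that the plan admits only symptoms as adverse events. It does not. What is missing is a prompt for signs in 4.2 and a limit saying which values qualify. The case report form and the content of Table 1 were not available for this check. If they already prompt for signs, that part becomes a wording change.
- **The selection rule is narrow.** A reader might infer that it also removes bradycardia and desaturation. It covers blood pressure only; heart rate and oximetry have no such rule and stay in the data.
- **The criterion is accuracy, not normality.** A low reading judged accurate is kept, and dropping a true artefact is reasonable. What does not stand is leaving no trace of the discarded value, because the judgement can then never be reviewed.
- **The clinician is blinded.** A reader might infer bias towards lidocaine. Sections 3.1 and 9.1.2 do not support that, unless drug effects reveal the assignment. Equal loss is still not neutral when the aim is to show similarity.
- **Important events have other routes.** Treated or serious events, naloxone use and changes of disposition are compared under 6.2, and the toxicity course described in 9.4.2 is symptomatic.
- **The hypotension had a context.** It occurred in three of ten cardiac surgery patients given 3 mg/kg together with several other drugs. It shows why blood pressure matters, and says nothing about the rate to expect here.

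**Conclusion.** The point holds in a limited form. An abnormal blood pressure can be lost from the record under 5.1.2. Symptomless, untreated, non-serious hypotension, bradycardia or desaturation can stay out of the by-arm comparison, because 4.2 does not prompt for signs and Section 6 plans no vital-sign summary. For heart rate and oximetry this is a gap in the analysis, not a loss of data.

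Any loss is expected to be similar in both arms, provided the blind holds. It would then shrink the observed difference and make similar safety easier to conclude. Its size cannot be estimated, because the documents give no rate of abnormal readings, of repeats or of discarded values. A reader might want to attach a number of lost patients; the documents offer nothing to base one on.

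**What to change.** 1. In 5.1.2, document every blood pressure reading with its time and the reason for the repeat. Use the first scheduled reading for time-point summaries, and let the clinician mark a reading as suspected artefact instead of replacing it.
2. In 4.2.2 to 4.2.8, change the adverse event item from new symptoms to new signs or symptoms, with a reference to 8.3.
3. Before unblinding, have the sponsor set the limits that define an abnormal vital sign. Add to 6.2.4 a by-arm summary of abnormal values with exact 95% confidence intervals (the interval type already planned there), given with and without readings judged to be artefact.

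The cost is a few extra fields on the form and a short addition to the analysis text. No additional measurements are needed and treatment is unchanged. Some artefact readings will be listed, and adverse event rates may rise slightly in both arms. Item 1 is the most urgent, since readings not documented during the trial cannot be restored later.
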